For the first 5 days during the Dosing and Follow-up Period, subjects will be admitted to an inpatient facility. Dosing will be staggered within and between cohorts, but the end of study for each individual subject is anticipated to be Day 200 or the time point at which complement activity has normalized, if later than Day 200.

Cohort	N	Study Drug	Route (SC/IV)	Planned Dose
1	6	ravulizumab	SC	400 mg
2	12	ravulizumab/rHuPH20	SC	500 mg/10,000 units
3	12	ravulizumab/rHuPH20	SC	1000 mg/20,000 units
4	12	ravulizumab/rHuPH20	SC	2000 mg/40,000 units
5	6	ravulizumab	IV	400 mg

Table 4: ALXN1210-HV-105 Study Design

Abbreviations: IV = intravenous; N = number [of subjects]; rHuPH20 = recombinant human hyaluronidase PH20; SC = subcutaneous.

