4.4. End of Study Definition

A subject is considered to have completed the study if he/she has completed all visits of the study including the last scheduled visit specified in the Schedule of Activities (Table 1 and Table 2).

The end of the study is defined as the last scheduled visit for the last subject, specified in the Schedule of Activities (Table 1 and Table 2). No further study assessments beyond CH50 evaluation, as needed based on individual subject results, will be performed after Day 200.

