6.6. Contraception Guidance

Female subjects who are documented as being of non-childbearing potential as defined in Section 10.4 (Appendix 4) are exempt from contraception requirements.

Female subjects of childbearing potential, if heterosexually active, must use highly effective or acceptable contraception as defined below. Antibiotic prophylaxis is required during this study, which can compromise the efficacy of hormonal contraception. Therefore, subjects using hormonal contraception must also use barrier contraception (eg, condom or diaphragm with spermicide) for the duration of antibiotic prophylaxis.

Highly effective contraceptive methods for females are as follows:

- Combined (estrogen- and progestogen-containing) hormonal contraception associated with inhibition of ovulation as follows:
 - Oral
 - Intravaginal
 - Transdermal
- Progestogen-only hormonal contraception associated with inhibition of ovulation as follows:
 - Oral
 - Injectable
 - Implantable

- Intrauterine device
- Intrauterine hormone-releasing system
- Bilateral tubal occlusion

Male subjects, if heterosexually active and with a female spouse or partner of childbearing potential or a pregnant or breastfeeding spouse or partner, must agree to use barrier contraception (male condom). Barrier contraception is required even with documented medical assessment of surgical success of a vasectomy. Female spouses or partners of male subjects who are of childbearing potential must use highly effective contraception as defined above, or acceptable contraception as defined below. Male subjects must not donate sperm and female subjects must not donate ova.

Acceptable contraceptive methods are as follows:

• Simultaneous use of male condom and, for the female partner, occlusive cap (diaphragm or cervical/vault caps) with intravaginally applied spermicide

Contraception must start during screening and continue after the end of the systemic exposure of the study drug as specified below:

- Cohorts 1 and 5 contraception must continue for at least 6 months after last dose. Male subjects must not donate sperm and female subjects must not donate ova until at least 6 months after last dose.
- Cohorts 2, 3, and 4 contraception must continue for at least 8 months after last dose. Male subjects must not donate sperm and female subjects must not donate ova until at least 8 months after last dose.

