8.3. Adverse Events and Serious Adverse Events

The definitions of an AE or SAE and specific reporting requirements are located in Section 10.3 (Appendix 3). Adverse events will be reported to the Investigator or qualified designee by the subject (or, when appropriate, by a caregiver, surrogate, or the subject's legally authorized representative).

The Investigator and any qualified designees are responsible for detecting, documenting, and recording events that meet the definition of an AE or SAE and remain responsible for following up AEs that are serious, considered related to the study drug or study procedures, or that caused the subject to discontinue the study drug (see Section 7).

8.3.1. Time Period and Frequency for Collecting Adverse Event and Serious Adverse Event Information

All AEs and SAEs will be collected from the signing of the ICF until the last follow-up visit.

Medical occurrences that begin before the start of study drug and after obtaining informed consent will be recorded on the eCRF, and will be considered as medical history.

All SAEs will be recorded and reported to the Sponsor or designee within 24 hours, as indicated in Section 10.3 (Appendix 3). The Investigator will submit updated SAE data to the Sponsor within 24 hours of the data being available.

Investigators are not obligated to actively seek AEs or SAEs after the conclusion of study participation (ie, after Day 200).

The method of recording, evaluating, and assessing causality of AEs and SAEs and the procedures for completing and transmitting SAE reports to Sponsor are provided in Section 10.3 (Appendix 3).

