8.3.5. Pregnancy

- Incidence of all pregnancies in female subjects and if indicated female sexual partners of male subjects will be collected after the administration of study drug and for at least 6 months (Cohorts 1 and 5) or 8 months (Cohorts 2, 3, and 4) thereafter.
- Complications of abnormal pregnancy outcomes (eg, spontaneous abortion, fetal death, stillbirth, congenital anomalies, and ectopic pregnancy) are AEs and may meet the criteria for SAEs (Section 10.3 [Appendix 3]).
- If a pregnancy is reported, the Investigator should inform the Sponsor within 24 hours of learning of the pregnancy. Specific pregnancy information to be collected is outlined in Section 10.4 (Appendix 4).

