8.6. Pharmacodynamics

After study drug administration, whole blood samples will be collected for measurement of serum free C5 concentrations, chicken red blood cell (cRBC) hemolytic activity, and potentially other measures of C5 activation as specified in the Schedule of Activities (Table 1 and Table 2). Additional samples may be collected during the study if warranted and agreed upon between the Investigator and the Sponsor.

Serum samples will be collected at baseline and during follow-up for measurement of CH50 activity using an in vitro LIA to confirm normalization of complement activity. If a normal CH50 result is obtained from a subject's first CH50 sample collected during follow-up, antibiotic prophylaxis can be stopped and the second scheduled CH50 sample is not required. If the first and second CH50 samples are not normal, the baseline sample may be analyzed, and further CH50 samples will be taken until complement activity has been normalized.

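### Section 8.3.1 ends active adverse event seeking at Day 200, although Section 4.1 keeps a late-normalising subject on study beyond it

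*Protocol*

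**What the plan says.** **Individual end of study.** Protocol Section 4.1 states that it "is anticipated to be Day 200 or the time point at which complement activity has normalized, if later than Day 200". The synopsis (Section 1.1), the schema note and SAP Section 3.2 carry the same rule.

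**CH50 follow-up.** Section 8.6 provides that, if the first two follow-up samples are not normal, "further CH50 samples will be taken until complement activity has been normalized". No upper day limit is given.

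**Safety collection.** Section 8.3.1 opens with: "All AEs and SAEs will be collected from the signing of the ICF until the last follow-up visit". Later in the same section: "Investigators are not obligated to actively seek AEs or SAEs after the conclusion of study participation (ie, after Day 200".

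**Permitted activity after Day 200.** Section 4.4: "No further study assessments beyond CH50 evaluation, as needed based on individual subject results, will be performed after Day 200".

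**Infection risk.** Section 2.3.1 names meningococcal infection as a risk of complete terminal complement inhibition. It commits to close watch of every subject for infection for as long as the study lasts.

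**Analysis.** SAP Section 4.12.1 defines a treatment-emergent event by its start after dosing and sets no end date. SAP Section 4.12 makes the safety analysis descriptive.

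**The concern.** The protocol uses two different ends of participation for the same person. Under Section 4.1 a subject whose complement has not recovered is still in the study after Day 200. Under Section 8.3.1 that subject's participation is over for the purpose of seeking adverse events.

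The only subjects with planned contact after Day 200 are those whose complement is not yet normal. They are the ones still carrying the risk that Section 2.3.1 singles out. As the text stands, such a subject attends, gives a CH50 sample and may leave without being asked about fever, infection or any other new event. Safety and tolerability is a primary objective, so the collection window should not depend on which section a site happens to read. What is at stake is mainly subject protection and a clear rule for the site. There is also an analysis question: an event volunteered after Day 200 would count as treatment-emergent under the SAP, while an unsolicited one would never be recorded.

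**Working it through.** **1. The plan's own basis for Day 200.** Section 4.2 says that 200 days is nearly 5 half-lives, with a half-life of about 42 days at the highest subcutaneous dose.

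- Half-lives elapsed: 200 / 42 = 4.76, so the statement reproduces.
- Fraction remaining, assuming mono-exponential decline: 0.5^(200/42) = 0.037, or 3.7%.
- Five full half-lives: 5 × 42 = 210 days.
- Planned duration: (70 + 200) / 7 = 38.6 weeks, which matches the stated 39 weeks.

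**2. Sensitivity to the half-life.** The values below other than 42 days are assumptions; the documents give only 42.

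| Half-life (days) | Half-lives in 200 days | Fraction left |
|---|---|---|
| 35 | 5.7 | 1.9% |
| 42 | 4.8 | 3.7% |
| 50 | 4.0 | 6.3% |
| 60 | 3.3 | 9.9% |

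**3. Can the number of late normalisers be found?** No. That needs a concentration at which CH50 recovers, or a recovery rate, and the documents give neither. Two bounding calculations show how far one can go. Both assume linear elimination at 42 days, equal bioavailability and the planned doses.

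- The Cohort 4 dose is 2000 / 500 = 4 times the Cohort 2 dose, so it stays above any given concentration log2(4) = 2 half-lives longer: 2 × 42 = 84 days. A Cohort 4 subject would be inhibited at Day 200 only if the same subject on the Cohort 2 dose would normalise at Day 200 − 84 = Day 116 or later.
- Section 2.3.1 places CH50 testing at about the time recovery is expected, and Table 2 schedules it on Days 43 and 57. If Day 57 is taken as Cohort 2 recovery, Cohort 4 recovery is Day 57 + 84 = Day 141, before Day 200. Day 57 is a planned check and not a guaranteed recovery date; Table 2 allows later samples.

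So the documents point to few late normalisers, most plausibly in Cohort 4, and do not exclude them. The if-later clause in Section 4.1 shows that the sponsor provides for them.

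**4. The sections side by side, for a subject not normalised at Day 200.**

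| Question | Section | Answer |
|---|---|---|
| Still on study? | 1.1, 4.1, schema, SAP 3.2 | Yes |
| CH50 sampling continues? | 8.6 | Yes |
| Infection watch applies? | 2.3.1 | Yes, while on study |
| Active seeking of events required? | 8.3.1 | No |
| Assessments other than CH50? | 4.4 | None |

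The first three answers cannot be squared with the last two.

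**The case against.** The strongest reply is that the gap is one of wording. Not being obliged to seek events does not forbid asking. The opening sentence of Section 8.3.1 runs to the last follow-up visit, and Section 8.6 speaks of CH50 samples taken in follow-up, so a late CH50 visit can be read as inside the window. Other safeguards continue. Events already reported as serious are followed to resolution (Section 8.3.3). Safety risks are discussed at each visit (Table 2). Antibiotic compliance is monitored daily (Section 8.2.9), and subjects carry a safety card (Section 8.2.10). Section 4.2 expects complement to be restored by Day 200.

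Much of this stands. It would be wrong to say that late subjects may not be asked or are left unprotected. But none of these provisions requires new events to be solicited after Day 200. The favourable reading of Section 8.3.1 also has to survive its own later sentence and Section 4.4.

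Two stronger inferences are tempting and are not supported.

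- A reader might infer that the gap biases the safety comparison between cohorts. The analysis is descriptive, and a common Day 200 cut-off gives completing subjects equal observation time. Asking only late normalisers would itself lengthen ascertainment unequally, so the fix must deal with that.
- A reader might take the Section 6.6 rule for Cohorts 2 to 4, that "contraception must continue for at least 8 months after last dose", as proof that exposure past Day 200 is planned. Section 6.6 describes contraception as outlasting systemic exposure, so the 8 months may include a margin. Section 4.2 expects complete elimination over the 200 days.

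**Conclusion.** The contradiction is real and sits in the current text. Sections 1.1, 4.1, the schema and SAP Section 3.2 extend an individual's study to complement normalisation; Sections 8.3.1 and 4.4 stop all but CH50 at Day 200. A subject still inhibited after Day 200 need not be asked about new adverse events while still on study and at the identified infection risk.

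The size is unknown. The number of such subjects cannot be computed from the documents. It is probably small, and it is most plausibly concentrated in the highest-dose cohort if that cohort receives its planned dose. The case rests on internal consistency and subject protection; it does not rest on a demonstrated effect on the results.

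Pregnancy collection is a separate, minor matter. Section 8.3.5 runs "for at least 6 months (Cohorts 1 and 5) or 8 months (Cohorts 2, 3, and 4) thereafter". Eight months is 8 × 30.4375 = 243.5 days, which is 43.5 days beyond the last scheduled visit. A reader might infer that all 36 subjects in Cohorts 2 to 4 are affected. However, collection concerns female subjects and, where indicated, partners of male subjects, whose number is not given, and the section works from reported pregnancies. The documents do not establish a need for a further contact with every subject.

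**What to change.** 1. **Section 8.3.1.** Replace the parenthesis that names Day 200 with: *the subject's end of study as defined in Section 4.1 (Day 200, or the visit at which complement activity has normalised, if later)*.
2. **Section 4.4.** Allow enquiry about adverse events, serious adverse events and concomitant medication at any CH50 visit after Day 200.
3. **SAP Section 4.12.1.** Keep the between-cohort tables of treatment-emergent event incidence to the common window through Day 200, and list later events separately. Without this, the first two changes would lengthen observation only for late normalisers.
4. **Separately.** Reconcile Sections 8.3.5 and 8.3.1 with the Schedule of Activities on how pregnancies are collected after Day 200.

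The cost is wording in the protocol and SAP, a few questions at visits that already take place, and a slightly later last data point for a few subjects. No dose or treatment rule is touched.

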8.3.2. Method of Detecting Adverse Events and Serious Adverse Events

Care will be taken not to introduce bias when detecting AEs and/or SAEs. Open-ended and nonleading verbal questioning of the subject is the preferred method to inquire about AE occurrences.

8.3.3. Follow-up of Adverse Events and Serious Adverse Events

After the initial AE/SAE report, the Investigator is required to proactively follow each subject at subsequent visits/contacts. All SAEs will be followed until resolution, stabilization, the event is otherwise explained, or the subject is lost to follow-up (as defined in Section 10.3 [Appendix 3]). Further information on follow-up procedures is provided in Section 10.3 (Appendix 3).

8.3.4. Regulatory Reporting Requirements for Serious Adverse Events

- Prompt notification by the Investigator to the Sponsor of a SAE is essential so that legal obligations and ethical responsibilities towards the safety of subjects and the safety of a study drug under clinical investigation are met.
- The Sponsor has a legal responsibility to notify both the local regulatory authority and other regulatory agencies about the safety of a study drug under clinical investigation. The Sponsor will comply with country-specific regulatory requirements relating to safety reporting to the regulatory authority, Institutional Review Boards (IRB)/Independent Ethics Committees (IEC), and Investigators.
- The Council for International Organizations of Medical Sciences or MedWatch reports must be prepared for suspected unexpected serious adverse reactions according to local regulatory requirements and Sponsor policy and forwarded to Investigators as necessary.
- An Investigator who receives an Investigator safety report describing a SAE or other specific safety information (eg, summary or listing of SAEs) from the Sponsor will review and then file it along with the IB and will notify the IRB/IEC, if appropriate according to local requirements.

8.3.5. Pregnancy

- Incidence of all pregnancies in female subjects and if indicated female sexual partners of male subjects will be collected after the administration of study drug and for at least 6 months (Cohorts 1 and 5) or 8 months (Cohorts 2, 3, and 4) thereafter.
- Complications of abnormal pregnancy outcomes (eg, spontaneous abortion, fetal death, stillbirth, congenital anomalies, and ectopic pregnancy) are AEs and may meet the criteria for SAEs (Section 10.3 [Appendix 3]).
- If a pregnancy is reported, the Investigator should inform the Sponsor within 24 hours of learning of the pregnancy. Specific pregnancy information to be collected is outlined in Section 10.4 (Appendix 4).

8.3.6. Management of Potential Adverse Events During Study Drug Administration

Infusion of other monoclonal antibodies has been associated with infusion reactions, with onset typically during or shortly after completion of the infusion. For this reason, subjects will be carefully observed during each infusion.

Subjects will be closely monitored during and after study drug administration for any symptoms of anaphylaxis and other hypersensitivity reactions, including circulatory and/or respiratory changes or arrest, or urticaria, arthralgias, myalgias, or other signs of related reactions. Adequate treatment will be immediately available. Infusion-associated AEs may occur, and depending on their type and severity, discontinuation of infusion may be required. Subjects will be informed of early symptoms and signs of hypersensitivity reactions including hives, swollen face, eyelids, lips, or tongue, or trouble with breathing. An acute infusion reaction algorithm will be used to manage infusion-related reactions (Section 10.7 [Appendix 6: Acute Infusion Reactions Algorithm]). In this study, regular assessments to monitor infusion reactions and infusion-site reactions will be done. To ensure that reactions can be dealt with promptly, there will be at least 15 minutes between the end of IV/SC infusion in 1 subject and the start of IV/SC infusion in the next subject. No more than 6 subjects assigned to receive ravulizumab IV will be dosed per day. Any reactions will be treated and taken into account in the dose continuation/escalation and toxicity rules (Table 7). If anaphylactic reactions occur, the current "UK Treatment Guideline for Anaphylactic Reactions" of the UK Resuscitation Council will be followed (Section 10.7 [Appendix 7: United Kingdom Resuscitation Council Anaphylaxis Algorithm]).

Subjects who experience a severe reaction during administration of study drug that results in discontinuation of study drug should undergo all scheduled safety, immunogenicity, PK, and PD evaluations required by the protocol. Subjects will therefore be instructed to attend all scheduled visits and undergo all procedures per protocol.

8.3.7. Study Drug Administration Reactions

8.3.7.1. Infusion-site Reactions

Infusion-site reactions are defined as AEs localized to the site of IV or SC route of study drug administration, occurring at any time during study participation that are assessed by the Investigator to be possibly, probably, or definitely related to study drug.

8.3.7.2. Infusion-associated Reactions

Infusion-associated reactions are defined as systemic AEs (eg, fever, chills, flushing, alterations in heart rate and blood pressure, dyspnea, nausea, vomiting, diarrhea, and generalized skin rashes) occurring during or within 24 hours of the start of IV or SC infusion that are assessed by the Investigator to be possibly, probably, or definitely related to the study drug.

8.4. Treatment of Overdose

No cases of overdose have been reported during ravulizumab IV or SC clinical studies. A single dose of study drug will be administered and monitored by site personnel.

8.5. Pharmacokinetics

Whole blood samples will be collected for measurement of serum concentrations of study drug as specified in the Schedule of Activities (Table 1 and Table 2). Additional samples may be collected during the study if warranted and agreed upon between the Investigator and the Sponsor. The actual date and time (24-hour clock time) of each sample will be recorded. Additional details, including further handling and processing instructions and sampling time windows will be provided in the study laboratory manual.

8.6. Pharmacodynamics

After study drug administration, whole blood samples will be collected for measurement of serum free C5 concentrations, chicken red blood cell (cRBC) hemolytic activity, and potentially other measures of C5 activation as specified in the Schedule of Activities (Table 1 and Table 2). Additional samples may be collected during the study if warranted and agreed upon between the Investigator and the Sponsor.

Serum samples will be collected at baseline and during follow-up for measurement of CH50 activity using an in vitro LIA to confirm normalization of complement activity. If a normal CH50 result is obtained from a subject's first CH50 sample collected during follow-up, antibiotic prophylaxis can be stopped and the second scheduled CH50 sample is not required. If the first and second CH50 samples are not normal, the baseline sample may be analyzed, and further CH50 samples will be taken until complement activity has been normalized.

8.7. Genetics

Genetics will not be evaluated in this study.

8.8. Biomarkers

Biomarkers will not be evaluated in this study.

8.9. Medical Resource Utilization and Health Economics

Medical resource utilization and health economics data will not be evaluated in this study.

9. STATISTICAL METHODS AND PLANNED ANALYSES

9.1. Statistical Hypotheses

Not applicable.

9.2. Sample Size Determination

The sample size is based on PK rather than statistical considerations. A total sample size of 48 subjects (6 subjects each in the control cohorts [Cohort 1 and 5] and 12 subjects each in the combination cohorts [Cohorts 2, 3, and 4]) will serve to estimate bioavailability.

9.3. **Populations for Analyses**

The analysis sets are defined in Table 8.

Set	Description	
Safety	All subjects who receive at least 1 dose of study drug	
Pharmacokinetic	All subjects who have sufficient serum concentration data to enable the calculation of PK parameters	
Pharmacodynamic	All subjects who have sufficient total and free C5 concentration data and cRBC hemolysis data which will enable the evaluation of the PD effects	
Immunogenicity	All subjects who have a predose and post-dose ADA sample collected	

Table 8: Study ALXN1210-HV-105 Analysis Sets

Abbreviations: ADA = antidrug antibody; C5 = complement component 5; cRBC = chicken red blood cell; PD = pharmacodynamic(s); PK = pharmacokinetic(s).

